5.1 Study Design

We will enroll up to 40 individuals with a below-knee amputation on only one side, who use their as-prescribed prosthesis on a regular basis. Three different prosthetic systems will be compared: (1) their as-prescribed prosthesis, (2) a new-to-market prosthesis with a unique liner with holes in it that allows sweat to flow away from the skin, and (3) a novel prosthesis that has a body-weight activated pump to create air flow between the prosthesis and the skin. After baseline and prosthetic fitting visits, participants will be randomized to use one of the two study prostheses during their normal daily activities for 2-weeks and then return to the VA for a data collection visit. This process will be repeated with their as-prescribed prosthesis, and then with the other study prosthesis.

See section 5.5 below for data collection procedures.

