When the treadmill walk is done, we will have participants sit and rest in a space with a comfortable climate (68 °F/20 °C, 50% relative humidity) for up to 30 minutes, and we will measure the prosthetic liner slippage. Participants will be asked to take off the prosthesis and then we will re-weigh the key components. We will also dry off participants' residual limb with an absorbent towel to collect the sweat remaining on the skin and remove the absorbent pad from the other leg. We will weigh the towels, prosthetic components, socks, and absorbent pad to see how much moisture the participants lost on their lower limbs by sweating.

We will put the step counter on participants' as-prescribed prosthesis. Participants will then be fit with their As-Prescribed prosthesis and asked to use it during their usual daily activities for the next two weeks.

Visits: As-Prescribed Prosthesis & Study Prosthesis 2

After the 2-week use period, participants will come back to the VA and, using their As-Prescribed prosthesis, they will do the same procedures they did with Study Prosthesis 1. At the end of the

visit, participants will be fit with the other study prosthesis then repeat the 2-week use period and the data collection visit.

During study sessions, visitors and observers will not be allowed in the lab unless the participant agrees to their presence; the participant can change her/his mind at any time.

Photos and Video

We may take video and photos of participants during portions of this study for documentation and use in research publications. To protect the identity and privacy of our participants, all videos and photos will be edited later to de-identify the images (e.g., blurring of faces, tattoos, and other distinguishing marks). No sound will be recorded to prevent voice identification.

Repository

Participants will be asked if they are interested in allowing their study data to be added to our de-identified data repository so that it may be used for additional research in the future. Participants who are interested will be asked to sign a separate consent form for the repository (MIRB# 00493). Once the consent form is signed, and after a PRAF to MIRB# 00493 to accept the data has been approved, a copy of the data will be added to the repository on an ongoing basis throughout the course of the study.

Payment to Participants

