5.6 Risks and Risk Management

Please note, the increase in physical risks associated with participation in this study only represent a small increase from those encountered in daily life of the participant population.

It is possible that participants may experience an injury (e.g., arising from a trip or a fall while walking on a treadmill or while wearing a study provided prosthesis during the at-home acclimation periods) and/or discomfort (e.g., mild to moderate muscle soreness, excessive skin dryness, blisters, or other soft tissue irritation while in the lab or during the at-home acclimation period), because of walking with the study-provided prostheses. It is possible that a component failure or malfunction of the prostheses could cause a soft tissue injury (e.g., soreness, bruising, scrape) or other minor mechanical injury (e.g., knee or ankle joint soreness). Care will be taken to properly fit the prostheses. Only trained study staff will place and remove the guaze for trapping moisture to mimimize risk of injury. Participants will only be asked to walk on the treadmill at a speed they are comfortable with. To minimize the risk of study prostheses failure, these devices will be thoroughly tested on a benchtop and a certified prosthetist will also evaluate the quality of the prostheses prior to them being worn by participants. Additionally, most of the prosthetic componentry are commonly used, commercially-available devices. Participants will be instructed to exhibit caution while acclimating to walking with a new or modified prosthesis, and they will be asked to check their skin for redness and/or skin irritation twice a day during the daily use periods. If skin issues arise participants will be instructed to contact study staff. These are the same instructions provided when a patient receives a new or different prosthesis as part of a clinical prescription. Since participants will have a chance to wear each of the study prostheses prior to wearing them home, we do not expect any problems to arise during the two-week at-home portion of the study. Participants will be asked to contact us immediately in the event of any study-related pain or injuries to schedule an examination.

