The PI will ensure the study procedures are being properly followed by keeping the research staff well informed of the current study procedures through regular/ongoing contact. Although an injurious fall or a prosthetic component failure related to this protocol is unlikely, we will tabulate a list of any such reports that occur during the study and compare it with corresponding data available in the literature. This will allow us to analyze how much of an increased risk was due to the administered protocol. After each report of an AE, SAE or an unanticipated problem, we will evaluate study procedures for previously-assessed risks, and will determine whether any changes to the protocol are necessary to minimize risks. The use of any procedures or equipment determined to be problematic will be suspended until these changes have been fully implemented and approved by the IRB.

Privacy and Confidentiality

See section 7.0 below for Information Security, Privacy, and Confidentiality related procedures.

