5.8 Withdrawal of Subjects

This is not a treatment study; withdrawing or being terminated from this study will not have an impact on participant safety. A study clinician or the PI may withdraw a participant without their consent if he or she feels that it is not in a participant's best interest to continue in the study or the person is unable to complete the study procedures. All data previously collected from participants who withdraw or are withdrawn will be kept and may be used in the study data analysis. Participants may withdraw at any time by informing the Research Coordinator and/or the PI. If a participant wants to withdraw or we choose to withdraw a participant, while she/he are using study equipment (i.e., one of the prostheses) we will arrange for the study prosthesis to be returned/removed and the participant's as-prescribed prosthesis to be re-fit.

6. Reporting

All safety information on AEs, SAEs, unanticipated events or problems, and protocol deviations will be collected. This information will be collected at study visits and whenever subjects call to report a problem. The information will be collected on VA IRB forms (Report of a SAE and/or Problem Form, or Report of Problems (ROP) Form) and in AE log forms as needed. Safety data will be collected on an as-needed basis and will begin upon enrollment into the study. All safety reporting requirements will be followed. Any anticipated AEs will be recorded on a log sheet and reported annually with the CRQ.

If we become aware of relevant findings or information that may affect subjects' health or welfare, we will contact subjects by phone and/or a letter to notify them.

Additional Safety Monitoring

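### The planned comparison of falls and component failures with unnamed literature cannot show the added risk of the protocol, and neither document plans to describe harm by prosthetic system

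*Protocol*

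**What the plan says.** Protocol section 5.6 introduces the events with "Although an injurious fall or a prosthetic component failure related to this protocol is unlikely". It continues "we will tabulate a list of any such reports that occur during the study and compare it with corresponding data available in the literature", then states "This will allow us to analyze how much of an increased risk was due to the administered protocol". No literature source, event definition, exposure measure or breakdown by prosthesis is given.

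The same section names other harms, among them "excessive skin dryness, blisters, or other soft tissue irritation while in the lab or during the at-home acclimation period". These are outside the listed comparison. On collection of safety information, section 6 says "This information will be collected at study visits and whenever subjects call to report a problem".

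Section 5.1 fixes the sequence. One study prosthesis is used first, and then "This process will be repeated with their as-prescribed prosthesis, and then with the other study prosthesis". Under section 5.5 the participant's own device is put through the same test: "using their As-Prescribed prosthesis, they will do the same procedures they did with Study Prosthesis 1". The home period on it is also two weeks ("asked to use it during their usual daily activities for the next two weeks"), with the step counter fitted.

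Section 5.7 and the SAP cover the efficacy, skin and comfort outcomes and, in the protocol, sweat rate and step count. Neither mentions falls, component failures or adverse events.

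**The concern.** The attribution sentence promises a quantity that the described method cannot give. A count without exposure cannot be set against a published rate. Read with the clause before it, the list covers events related to the protocol, and a list filtered in that way is not like for like with general fall or failure data. With no source named, comparability cannot even be checked.

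Separately, the trial asks which system gives a secure fit without harm to the limb, and hopes for wide uptake of the best one. One of the three systems is experimental. As planned, the report need not show whether falls, failures, blisters or irritation occurred on the experimental system, the perforated liner or the participant's own prosthesis. The design already holds a concurrent reference for that question, and no use of it is planned.

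**Working it through.** Neither document states a safety rate, safety sample size or safety power, so there is no figure of the plan's own to reproduce. The check has three parts.

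**1. What each comparison can address**

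| Comparison | What differs between the two sides | What it can address |
|---|---|---|
| Whole-study list against literature (planned, 5.6) | Participants, devices, setting, definitions and reporting may all differ; source and denominator not given | Whole-protocol risk at best, and only once source and exposure are supplied |
| Each study device against the same participants' as-prescribed period (not planned) | Device, place in the sequence, possibly reporting | Device-added risk only; risk from the protocol is on both sides and cancels |

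These are two different quantities, and neither comparison replaces the other.

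**2. How precise a by-system description would be**

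Inputs: N = 20 (sample size supported in section 5.7) or 40 (maximum enrolment, section 5.1); two weeks of home use per system (section 5.5); no dropout assumed.

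- Exposure per system = N × 2 weeks. N = 20: 40 person-weeks × 7/365.25 = 0.767 person-years. N = 40: 80 person-weeks = 1.533 person-years.
- Zero events on one device, one-sided 95% Poisson upper bound = −ln(0.05)/T. N = 20: 2.996/0.767 = 3.91 per person-year. N = 40: 2.996/1.533 = 1.95.
- The same as a proportion of participants, 1 − 0.05^(1/N): 13.9% at N = 20 and 7.2% at N = 40.
- Both study devices pooled: 80 person-weeks (1.53 person-years), bound about 2.0 per person-year at N = 20; 160 person-weeks (3.07 person-years), bound about 1.0 at N = 40. Pooling hides which device was involved.
- Paired test: with k discordant participants all in one direction, exact McNemar two-sided p = 2 × 0.5^k. Five give 0.0625 and six give 0.031, so at least six are needed.
- Example: 3 events against 1, with equal exposure, give a rate ratio of 3.0 with exact 95% interval 0.24 to 157.5.

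Power of the exact McNemar test at two-sided 0.05. The event proportions are assumptions, not in the documents, and events are taken as independent within a participant:

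| Study device vs as-prescribed | N = 20 | N = 40 |
|---|---|---|
| 10% vs 5% | 0.5% | 4% |
| 20% vs 5% | 9% | 39% |
| 30% vs 5% | 34% | 80% |

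**3. Ascertainment after the chamber walks**

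- Walk 1 (study prosthesis): followed by the as-prescribed visit.
- Walk 2 (as-prescribed): followed by the second study-prosthesis visit.
- Walk 3 (the other study prosthesis): no later scheduled contact. Section 5.5 allows an extra visit only for missing or corrupt data.

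So one of two study-prosthesis walks per participant relies on the participant calling, against none of the as-prescribed walks. Other features complicate the direction. Section 5.6 asks participants to report pain or injury that is study-related, which may under-count events on their own device. A delayed event after the as-prescribed walk would arise while the second study prosthesis is being worn. The documents do not settle the net bias.

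**The case against.** The strongest reply is that section 5.6 asks about risk from the protocol, and the as-prescribed period, with the same hot-chamber walk, is part of that protocol. A reader might infer that comparing with the as-prescribed period would deliver the promised quantity. It would not, so the literature comparison should stay, with its source named.

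Second, the reference period is imperfect. As-prescribed is always second, and participants have at least six months of prosthesis use behind them. Whether the twice-daily skin checks apply in that period is not explicit: section 5.5 refers to the daily use periods in general but introduces the checks with the study prostheses. These limits stand and must be stated with any contrast.

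Third, by-device tabulation is not ruled out; the documents are silent. A reader might infer that the sponsor chose not to separate harm by device, or that safety is unwatched. Neither is supported. All adverse events are collected (section 6), each report triggers a review of procedures (section 5.6), and the Medical Monitor reviews data quarterly. That protects participants but does not compare systems. Limb health is also compared across systems through hydration, transepidermal water loss and comfort (H2.1 to H2.3). Those measures do not count blisters, falls or failures.

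Fourth, the counts will be too small for a firm answer. That also stands, and it limits the table to description.

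**Conclusion.** The point holds in a limited form. The list in section 5.6 cannot support the attribution sentence, because it has no denominator, no device split and no identified comparable source. Neither document plans to describe device-added harm using the as-prescribed period already in the design.

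A by-system table is a real but modest improvement. With zero events on one device, rates up to about 3.9 per person-year (N = 20) or 2.0 (N = 40) stay compatible with the data. These bounds assume full two-week exposure, no dropout and Poisson events. A formal test would be informative only if the rates on the two systems differed widely.

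A reader might also infer that the missing contact after the third walk makes the study prostheses look safer. The documents show unequal ascertainment, but because of the opposing features above they do not show its net direction. None of this affects the analyses of slippage, perspiration, skin measures or comfort.

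**What to change.** In Protocol section 5.6 and the SAP:

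- Tabulate falls, component failures and skin events by system worn at onset (as-prescribed, Uniprox, DAE-RED) and by setting (home, chamber). Include all reported events, not only those judged study-related. Give participants affected, events, person-weeks and steps.
- Show the paired contrast of each study device with as-prescribed descriptively, with exact intervals. State that it addresses device-added risk only, that as-prescribed is always second, and that precision is low.
- Attribute events to the system worn at onset, except that events within a short pre-specified window after a chamber walk are flagged to the system worn in that walk. The window is essential: every home event in the second and third periods starts after some walk, so an open-ended rule would assign those events to the previous system.
- Keep the literature as external context for whole-protocol risk, name the source and its rate, and reword the attribution sentence so that it does not promise an estimate.
- State the unequal ascertainment after the third walk as a limitation or, if follow-up is still open, ask about events in one brief closing contact.

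The cost is a few sentences and one table from information largely collected already, provided that event logs carry onset dates, plus at most one short contact per participant. The SAP is written in the past tense, so the closing contact may no longer be possible; the table and rewording still are. The downside is small counts, so the result is descriptive only.

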5.7 Data Analysis

Data collected from the laboratory-based experiments will be used to test three hypotheses. The distance that the proximal border of the liner moved from its pre- to post-treadmill walk in the environmental chamber position (marked on the skin) will be compared and enable us to test hypothesis: (H_{1.1}) *The amount of slippage (loss of adherence) will be different between the three prosthetic systems.* The tare weight (wet – dry conditions) of perspiration expelled from Uniprox and DAE-RED prostheses will be compared and enable us to test hypothesis: (H_{1.2}) *The amount of perspiration expelled will be different between the Uniprox and DAE-RED.*

Data collected from the field-based experiments will be used to test three hypotheses. The mean result from the three measures of skin hydration from the posterior compartment of the residual limb will be compared and enable us to test hypothesis (H_{2.1}) *Residual limb skin hydration will be different between the three prosthetic systems.* The mean result from the three measures of transepidermal water loss from the posterior compartment of the residual limb will be compared and enable us to test hypothesis (H_{2.2}) *Residual limb transepidermal water loss will be different between the three prosthetic systems.* The Socket Comfort Score will be used to access the comfort of the three prosthetic systems and enable us to test hypothesis (H_{2.3}) *The Socket Comfort Score will be different between the three prosthetic systems.*

The statistical analysis to test these hypotheses will require six linear mixed effects regression analyses. These analyses will test for differences by prosthetic system (as-prescribed, Uniprox, DAE-RED) with random effects for subject and subject by prosthetic system interaction. The experiment-wise significance will be set a priori at an alpha level of $p<0.05$ and a Bonferroni adjustment will be applied for multiple comparisons. All analyses will be performed using existing software (R Foundation for Statistical Computing with lme4 and multcomp packages, Vienna, Austria). Exact p-values will be reported for each test.

Statistical Power Analysis

We conducted several power analyses to explore the statistical strength of our study design and estimate the number of subjects necessary to obtain meaningful results.

The first exploratory analysis uses liner slippage ($H_{1.1}$) as the metric of interest. In our current study, we fit participants with a modified PTB socket and two study prostheses: (1) a distal PIN locking liner and (2) a battery-powered dynamic air exchange (DAE) system. Subjects walked at their self-selected speed on a treadmill in our environmental chamber set to varying temperatures, including one condition at 35° C and 50% relative humidity. Liner slippage ($n=10$, interim results) was measured by marking the skin at the proximal border of the liner prior to the protocol and measuring the distance (mm) between the mark and the liner at the end of the protocol. Liner slippage was 23.6 ± 18.2 mm and 11.7 ± 20.0 mm while wearing the PIN and DAE systems, respectively. If we assume liner slippage while wearing the DAE-RED will be the same as the DAE, a reasonable assumption as the body-weight activated pump in DAE-RED generates the same vacuum levels with active subjects as the battery-powered pump in the DAE, then we calculate a 99 percent probably that the study will detect a difference between prostheses at $p<0.05$ with *10 subjects*.

A second exploratory power analysis for the skin hydration ($H_{2.1}$) metric was performed using published values from Firooz [36]. Using the same instrument (Corneometer CM825; Courage & Khazaka, Köln, GER) proposed in our study, Firooz measured skin hydration of subjects diagnosed with atopic dermatitis ($n=30$) and age-matched controls ($n=30$) at several upper body sites including the dorsal surface of the hand. Atopic dermatitis is a chronic, reoccurring, pruritic form of dermatitis prone to dry skin and other complications. Firooz found skin hydration of 38.9 ± 12.8 and 29.6 ± 10.0 (arbitrary units) for the control group and atopic dermatitis group, respectively. While Firooz's study used a between-subject experimental design, our proposed within-subject study can be expected to have less variance. If we assume a standard deviation of 12.8 for the difference between study prosthetic systems and a difference between means of 9.3, there is an 80% probability to find a significance difference between prosthetic systems with *17 subjects*. Choi [37] also used the same instrument to measure skin hydration, but at eight different anatomical sites including the leg posterior surface, on children with extrinsic atopic dermatitis ($n=41$) and age-matched controls ($n=8$). Choi found skin hydration of 64.8 ± 14.4 and 52.1 ± 14.2 (arbitrary units) for the control group and atopic dermatitis group, respectively. Choi also used a between-subject experimental design which

would likely have greater variance than our proposed within subject experimental design. Assuming a standard deviation of 14.4 for the difference between study prosthetic systems and a difference between means of 12.7, there is an 96% probability to find a significance difference between prosthetic systems with *20 subjects*.

A third exploratory power analysis for the transepidermal water loss ($H_{2.2}$) metric was performed, also using results reported by Choi [37]. Using the same instrument (Tewameter TM300; Courage & Khazaka, Köln, GER) proposed in our study, Choi measured transepidermal water loss as described above and found the transepidermal water loss of 16.5 ± 8.17 and 28.8 ± 18.8 g/m²/h for the controls and extrinsic atopic dermatitis children, respectively. If we assume a standard deviation of 13.0 for the difference between study prosthetic systems and a difference between means of 12.3, there is an 97% probability to find a significance difference between prosthetic systems with *20 subjects*. We note Choi reported a large difference in variances between groups (8.17 and 18.8 g/m²/h), and the power analysis is particularly sensitive to different variances. We used a value mid-way between the two groups; using a greater variance of 18.8 results in a 79% probability to find a difference with *20 subjects* while using a smaller variance of 8.17 results in a 99% probability to find a difference with *20 subjects*.

These analyses provide confidence that our proposed within-subject experimental design will provide meaningful results with a sample population of 20 subjects.

Supplemental Measures

Absorbent pads placed on the skin of the contralateral limb during the laboratory protocol will be used as a control measure of perspiration. The tar weight of the pad will be used to calculate the perspiration rate by dividing the weight of the pad by its surface area and the donned duration, expressed in grams per meter square of body surface area per hour (g m⁻² h⁻¹). We will perform a linear mixed effects regression analysis on these samples to determine if there were differences in perspiration rate across study prosthetic systems (independent variable). If a significant difference is found, we will perform an analysis of co-variance in consultation with our Center's biostatistician to quantify the effects on the study results.

The number of prosthetic steps taken over the two-week field protocol will be used as a control measure of activity and to verify participants are wearing the study prostheses. After wearing each study prosthesis in their home, work, and community environments while participating in their usual daily activities, the Fitbit Zip will be removed from the prosthetic pylon and synchronized with the Fitbit Dashboard. The prosthetic steps taken over the two-week period will be summed and compared. We will perform a linear mixed effects regression analysis on this data to determine if there were differences in activity across study prosthetic systems (independent variable). If a significant difference is found, we will perform an analysis of co-variance in consultation with our Center's biostatistician to quantify the effects on the study results.

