Title: Novel Lower-Limb Prostheses: Comparing Adherence, Perspiration, and Residual Limb Skin Health in a Hot, Humid Environment and During Activities of Daily Living

NCT03900845

Document Date: 10Apr2023

Statistical Analysis Plan

Linear mixed effects regression was used to assess the association between outcomes and suspension system. Study participant was modeled as random. Hypothesis testing was carried out using conditional F-tests. Results are summarized as means \pm standard error (SE) for each suspension system and mean differences among groups, \pm SE, 95% confidence intervals and p-values to test if pairwise differences were significant using Tukey's method to adjust for multiple comparisons. Differences from the baseline measurements were not assessed. Variables with heterogeneous variances were analyzed using log transformations with mean differences back transformed into the original units and pairwise differences presented as ratios. Significance was reported with a nominal threshold of $p < 0.05$, supplemented by effect sizes (Hedges' g). Effect sizes were interpreted as small ($0.2 \leq g \leq 0.5$), moderate ($0.5 \leq g \leq 0.8$), and large ($g \geq 0.8$) (Cohen, 2013). Analyses were carried out using R 4.2.1 (Team RC, 2022), and packages tidyverse, lme4, emmeans and kableExtra (Wickham, 2019; Bates, 2015; Lenth, 2022; Zhu, 2023).

Cohen J. Statistical power analysis for the behavioral sciences. New York, NY, Academic Press, 1977.

Team RC. R: A language and environment for statistical computing [Internet]. Vienna, Austria: R Foundation for Statistical Computing; 2022. Available from: www.R-project.org

Zhu H (2023). *kableExtra: Construct Complex Table with 'kable' and Pipe Syntax*. R package version 1.3.4.9000, <https://github.com/haozhu233/kableextra>.

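### Neither document is shown to deliver the protocol's experiment-wise 0.05, and the power figures omit the pairwise adjustment that both documents promise

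*Protocol*

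**What the plan says.** **Protocol, section 5.7.** The error rule is one sentence: "The experiment-wise significance will be set a priori at an alpha level of $p<0.05$ and a Bonferroni adjustment will be applied for multiple comparisons". No family, divisor or primary outcome is given. The sentence follows the description of mixed models that test for differences by prosthetic system, and the software is named next: "R Foundation for Statistical Computing with lme4 and multcomp packages".

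The counts in the same section disagree. It says "The statistical analysis to test these hypotheses will require six linear mixed effects regression analyses" and "Data collected from the laboratory-based experiments will be used to test three hypotheses", but labels only two laboratory hypotheses (H1.1, H1.2). It then says "Data collected from the field-based experiments will be used to test three hypotheses" and labels three (H2.1 to H2.3). That makes five hypotheses, which is also the number in section 3.

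**SAP.** The model statement is general: "Linear mixed effects regression was used to assess the association between outcomes and suspension system". Hypotheses are tested with conditional F-tests. Pairwise p-values test whether "pairwise differences were significant using Tukey's method to adjust for multiple comparisons". The threshold is given as "Significance was reported with a nominal threshold of" 0.05. The SAP does not mention Bonferroni, an experiment-wise level or any adjustment across outcomes, and it gives no reason for the change.

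**Protocol, Statistical Power Analysis.** Powers are given for skin hydration and transepidermal water loss, each for a difference between two systems. The section concludes that 20 subjects are enough.

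**The concern.** An experiment-wise claim tells the reader how often the whole set of tests would give a false positive. To be usable it needs a defined family, and the analysis has to control error over that family. Here the family is undefined, the two documents name different methods, and the SAP calls its threshold nominal.

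Two things are at stake. First, a reader who takes the protocol's wording at face value will credit any single significant outcome with more protection than the procedure gives. Secondly, a sample size justified at an unadjusted 0.05 overstates the power of the adjusted contrasts that will be reported.

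**Working it through.** **1. Reproduce the protocol's power figures.** Inputs are the mean differences and SDs of the difference stated in the power section. Sidedness is not stated; two-sided is assumed because the hypotheses say only that systems differ. For a paired t-test, the noncentrality is (difference/SD) × √n on n − 1 df, at alpha 0.05 with no adjustment. For hydration 9.3/12.8 at n = 17, the noncentrality is 0.727 × 4.123 = 3.00 and the power is 80.3%, against 80% stated.

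**2. Repeat with the SAP's Tukey contrasts.** The noncentrality is unchanged. The critical value is the studentized range for three systems divided by √2, on 2(n − 1) df: 32 at n = 17 and 38 at n = 20. The pooled error term assumes that the three between-system differences have equal variance.

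| Contrast | n | Stated | Unadjusted 0.05 | Tukey 0.05 |
|---|---|---|---|---|
| Hydration 9.3/12.8 | 17 | 80% | 80.3% | 70.3% |
| Hydration 12.7/14.4 | 20 | 96% | 96.2% | 92.9% |
| Water loss 12.3/18.8 | 20 | 79% | 79.3% | 68.6% |
| Water loss 12.3/13.0 | 20 | 97% | 98.0% | 95.9% |

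The first three rows match the unadjusted calculation and not Tukey. The fourth does not discriminate. The slippage power (99% with 10 subjects) cannot be checked, because no SD of the paired difference is given.

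**3. Compare the two methods within one three-system outcome, n = 20, 38 df.** Bonferroni over three pairs has critical t 2.505, and a chance of any false positive of 0.0431. Tukey has critical t 2.439, and a chance of 0.050. The difference is small.

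**4. Error across outcomes if the family is the pairs within each model.** Four outcomes compare three systems. H1.2 compares two, so it has one contrast at 0.05. With all nulls true and independent outcomes:

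- Protocol rule: 1 − (1 − 0.0431)^4 × 0.95 = 0.203.
- SAP rule: 1 − 0.95^5 = 0.226, with an upper bound of 5 × 0.05 = 0.25 under any dependence.

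The correlation between outcomes is not in the documents, so it was varied by simulation at n = 20:

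| Assumed correlation | 0 | 0.3 | 0.5 | 0.8 |
|---|---|---|---|---|
| Protocol rule (within model) | 0.203 | 0.191 | 0.171 | 0.130 |
| SAP rule | 0.226 | 0.211 | 0.188 | 0.143 |

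Using the conditional F-test alone as the decision rule gives the same values as the SAP row.

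**5. Error if the family is all hypotheses.** Bonferroni would use 0.05/5 = 0.010 or 0.05/6 = 0.0083, depending on which count is right. Five independent tests at 0.010 give 1 − 0.99^5 = 0.049. The SAP's rule still gives 0.226, or 1 − 0.95^6 = 0.265 with six tests.

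**The case against.** The strongest defence is that the adjustment was only ever meant for the pairs within a model. The Bonferroni sentence follows a description of testing between systems, multcomp is cited next, and the SAP uses the same multiple-comparisons phrase for pairwise differences. Powers set at an unadjusted 0.05 also suggest that no division across hypotheses was intended. This stands. It is the best-supported reading, and on it Tukey is a valid all-pairs method that gives up almost nothing.

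The five outcomes are also distinct, they fall under two aims, and no rule declares success if any one is significant. Control across outcomes is therefore a choice and not an obligation. The SAP openly writes nominal and adds intervals and effect sizes, and the protocol promises exact p-values. That stands too, but it does not rescue the term experiment-wise, and readers can correct for themselves only if told that nothing was done across outcomes and how many tests there were.

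Stronger inferences are tempting but not supported:

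- That the protocol held 5% across outcomes and the SAP raised it to 23%. This is true only if the family is all hypotheses, which the protocol never says.
- That the laboratory and field experiments are the families. The protocol uses those words for data sources and does not tie them to the error rate.
- That the set of significant results differs between the documents. It may, but no results are given.
- That the method was changed after the data were seen. The SAP is in the past tense and dated April 2023, so the analysis may already have been done, but the documents do not show when the choice was made.

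**Conclusion.** The point holds as a matter of clarity, disclosure and power reporting. On the best-supported reading, the label is wrong and the method is acceptable. Error is held at or just below 5% within each outcome, while the chance of any false positive across five outcomes is about 20% (protocol) or 23% (SAP) if they are independent, falling to 13% or 14% at an assumed correlation of 0.8. If the sponsor meant all hypotheses, the SAP drops the protocol's claim. No reading leaves both documents correct as written.

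The mismatch in counts may be a miscount or a dropped hypothesis; the documents do not show which. The power overstatement is 10 points for two of the stated figures and 3 for another. It does not by itself overturn the choice of 20 subjects: hydration 9.3/12.8 reaches 79% under Tukey at n = 20, although water loss with SD 18.8 stays at 69%. These powers concern pairwise contrasts; power of the overall F-test was not computed.

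**What to change.** 1. Replace experiment-wise with a statement that error is controlled at 0.05 within each outcome only, and not across the five outcomes. Report and interpret the findings that way.
2. Disclose the change from Bonferroni to Tukey, with the reason. If the analysis is already done, rewording cannot restore pre-specification, so the disclosure belongs in the report.
3. Reconcile the counts of models and hypotheses, and say whether a sixth hypothesis existed.
4. Restate the power figures under the Tukey contrasts, or label them as unadjusted.

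These changes cost wording and a short recalculation; trial conduct is untouched.

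If the sponsor did intend control across all hypotheses, the SAP must instead report p-values adjusted across the reconciled set. Bonferroni at 0.010 for five, with the Tukey contrasts at that same level, is one valid choice. The cost is power. At n = 20, moving Tukey from 0.05 to 0.01 takes hydration 9.3/12.8 from 79% to 56%, and water loss with SD 18.8 from 69% to 44%. Reaching 80% would then need 29 and 36 subjects with data. Both are below the enrolment ceiling of 40, but 36 leaves room for only four losses, and the option is closed if data collection has ended.
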